APPENDIX 3 - RISK/BENEFIT ASSESSMENT

Clinical Risk/ Benefit Assessment

SUMMARY

The cryoICE™ CryoAnalgesia study is being undertaken to examine pain management in post thoracic procedures via intercostal cryoanalgesia. Subjects meeting the inclusion/exclusion criteria and undergoing unilateral thoracotomy cardiac procedures will participate in this study. The risks of participation are offset by the significant potential for clinical and functional benefits.

POTENTIAL BENEFITS

The potential benefit to study subjects outweighs the risks of participation in this study.

The benefits may include but are not limited to, the following:

- Clinical improvement - patients may experience improved post-operative pain control following minimally invasive heart valve surgery
- Functional improvement - patients may experience less post-operative pulmonary complications, less mental status changes, improved blood pressure and heart rate
- Overall advancement of medical and scientific knowledge - Information obtained from this study may further our understanding of peri-operative pain control following this surgical procedure and improve patient post-operative experience.

There may also be other benefits that are unforeseen at this time.

POTENTIAL RISKS

Risk Category: Minimal

Independent from this research study, the participant is already scheduled to undergo a minimally invasive heart valve surgical procedure via right mini-thoracotomy. All risks for this procedure will have been discussed with the surgeon and surgical consent will have been signed. Similarly, common anesthetic risks will have been discussed, and anesthetic consent will have been signed. The participant will be fully informed of the risks of this study. Possible adverse events may include, but are not limited to, the following.

Risks of Intercostal Cryoanalgesia with the cryoICE® probe:

Most frequent (occurring more than 10% of the time):

- Device Breakage
- Skin injury due to cryoablation minor damage of skin that would heal over time
- Intercostal muscle injury
- Permanent peripheral nerve damage resulting in difference in sensation not evident prior to surgery
- Failure to ablate peripheral nerve may result patient requiring pain management

Less frequent (occurring 1-10% of the time):

- Tissue perforation
- Tissue freezing

Rare (occurring less than 1% of the time):

- Injury to user
- Nitrous gas exposure to patient

There may also be other risks that are unforeseen at this time.

MINIMIZATION OF RISKS

Measures which will be taken to minimize risks related to the study include:

- Investigators will be chosen that are qualified to complete study index procedures and are experienced in use of cryoICE cryo-ablation system.
- Well defined clinical study protocol, including specific inclusion/ exclusion criteria to enroll appropriate subjects in the trial.
- Close patient monitoring during the surgical procedure and follow-up period.

Alternative to Participation:

Patients may decline and would be treated with the same standard of care.

CONCLUSION

This clinical study is justified because the study sponsor and clinical investigators believe the potential benefits outweigh the potential risks.

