Indication of Device:	
All medical devices used during this study are cleared for commercial distribution and are to be used in accordance with approved product labeling.
 
AtriCure's cryoICE™ cryo-ablation probes are sterile, single use devices intended for use in the cryosurgical treatment of cardiac arrhythmias by freezing target tissues, creating an inflammatory response (cryonecrosis) that blocks the electrical conduction pathway. The probe is also intended for use in blocking pain by temporarily ablating peripheral nerves.
 
The PROBE may be used in conjunction with a standard off-the-shelf nerve stimulator device in applications where precise peripheral nerve location is desired.

Study Objectives:	
The objectives of this study are to:
 
 1. To demonstrate that intraoperative intercostal cryoanalgesia provides improved analgesic efficacy in patients undergoing unilateral thoracotomy cardiac procedures as compared to current intraoperative standard of care. 2. Long-term goal is to elucidate complementary strategies for enhanced postoperative pain management of patients at risk for postoperative pulmonary complications from unilateral thoracotomy cardiac procedures. 
Completion of the proposed study will for the first time demonstrate efficacy of intercostal cryoanalgesia in patients undergoing minimally invasive cardiac procedures. Furthermore, results of this study may have a pivotal role in supporting future clinical outcome trials for intercostal cryoanalgesia therapy.

Number of Subjects (Planned):	Up to 100 subjects will be randomized into this study
Sites:	Up to 5 sites

Patient Population:	Patients undergoing unilateral thoracotomy cardiac procedures
Inclusion Criteria:	
Patients satisfying the following criteria will be considered the screening population and will be eligible for participation:
 
 1. Age 18 - 85 years male or female 2. Patients undergoing unilateral thoracotomy cardiac procedures (with the exception of Aortic Aneurysm repair as sole treatment) 3. Acceptable surgical candidate, including use of general anesthesia 4. Willing and able to provide written informed consent 5. Willing and able to return for scheduled follow-up visits

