Recent studies have demonstrated the beneficial effect of cryoanalgesia for post-thoracotomy pain in reduction of opioid requirement, reduction in post-operative pain scores, superior hemodynamic recovery (optimization of systolic blood pressure and heart rate, optimization of the pH values of arterial blood gases, and superior pulmonary function (higher FEV₁ and FVC values).¹ Intercostal cryoanalgesia can produce temporary neurolysis for up to two months without long-term histological nerve damage.²

We propose to assess whether intra-operative intercostal cryoanalgesia using the *cryoICE®* probe [REDACTED] provides superior post-operative analgesic efficacy as compared to current pain management in patients undergoing unilateral thoracotomy cardiac procedures.

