10.0 Safety Monitoring

Subject safety will be monitored throughout the course of this study by monitoring for Adverse Events and Product Complaints related to the AtriCure *cryoICE* Probe (CRY02) used in conjunction with the *cryoICE* BOX (v6). The AtriCure *cryoICE* Probe (CRY02) used during the index procedure for the clinical study has been cleared for marketing by the FDA and is being used within the current labeling and indications for use. Any event that occurs that may have caused or contributed to a death or serious injury or that indicates the AtriCure *cryoICE* Probe (CRY02) device has malfunctioned and would be likely to cause or contribute to a death or serious injury if the malfunction were to recur will be reported in compliance with 21 CFR Part 803.

In addition to general surgical risks, additional risks specifically associated with the AtriCure *cryoICE* Probe (CRY02) are as follows:

- Skin injury due to cryoablation of skin
- Intercostal muscle injury
- Permanent peripheral nerve damage

These risks could lead to symptoms that include:

- Numbness around the incision lasting from 1 to 6 months
- Neuralgia occurring 6 weeks after cryoanalgesia, lasting up to 2 months
- Hyperesthesia

There may also be other risks that are unforeseen at this time. The complete Risk/Benefit Assessment is found in Appendix 3.

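### Appendix 3 puts permanent nerve damage above 10%, unsourced and under a minimal-risk label, in conflict with other sections; lasting sensory loss is not systematically measured in both arms

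*Combined protocol and SAP*

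**What the plan says.** **Frequency and label.** Under Potential Risks, Appendix 3 gives the overall label "Risk Category: Minimal". Its top band is headed "Most frequent (occurring more than 10% of the time" and contains "Permanent peripheral nerve damage resulting in difference in sensation not evident prior to surgery". No study, count or denominator is cited for the band.

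**Permanence elsewhere.**
- Synopsis, Indication of Device: "The probe is also intended for use in blocking pain by temporarily ablating peripheral nerves".
- Section 1.0: "Intercostal cryoanalgesia can produce temporary neurolysis for up to two months without long-term histological nerve damage".
- Section 10.0 lists "Permanent peripheral nerve damage" as a device-specific risk, with no frequency. Among the symptoms that the listed risks could cause, it gives "Numbness around the incision lasting from 1 to 6 months".

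**Seriousness.** Section 10.2.1 counts an adverse event as serious if, among other criteria, it leaves permanent damage.

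**Measurement.**
- Allodynia at 3 and 6 months is a secondary endpoint (Sections 3.0 and 9.2), compared between arms in Section 9.6.1.
- The 90- and 180-day calls include allodynia screening and an adverse event assessment (Sections 7.7 and 7.8).
- A cotton-tip examination follows only if the screen is positive (Section 7.10). Appendix 2 allows two responses, normal sensation or sudden sharpness, and counts only sharpness as positive.
- All adverse events go into source documents, but only those related to cryoanalgesia or the device go on the eCRF (Sections 7.11 and 10.2.4). Section 9.6.2 summarises these descriptively for the Study Group.

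**The concern.** An ethics board or investigator reading Appendix 3 meets a permanent injury expected in more than one treated subject in ten, beneath a minimal-risk label. Other sections describe an effect that wears off. The reader cannot tell whether the band, the word permanent or the risk category is mistaken. Three quarters of subjects are allocated to the device and Section 12.1 foresees no independent oversight, so the written risk statement carries more weight than usual.

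The trial is also a natural place to learn how often sensation stays altered, because it has a randomised control arm and calls at 90 and 180 days. Section 1.0 says that thoracotomy itself disrupts neurovascular bundles, so numbness can occur in either arm. Without a control count, the share due to cryoanalgesia rests on each investigator's judgement of relatedness.

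**Working it through.** **1. Can the band be reproduced?** No. The documents give no numerator, denominator or source for it. It is also the only frequency given for nerve damage, so the conflict is between one number and several qualitative statements.

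**2. The statements side by side.**

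| Place | Duration | Frequency |
|---|---|---|
| Synopsis, Indication of Device | temporary ablation | none |
| Section 1.0 | temporary, up to two months; no long-term histological damage | none |
| Section 10.0, risk list | permanent | none |
| Section 10.0, symptom list | numbness 1 to 6 months | none |
| Appendix 3 | permanent, with changed sensation | above 10% |

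Section 10.0 and Appendix 3 agree that permanent damage is possible. They do not agree on what follows from it, since Section 10.0 pairs a permanent injury with time-limited numbness. Only Appendix 3 says that it is common.

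**3. What the band implies if taken literally.** Inputs: n = 75 planned Study Group subjects (Section 9.3) and p = 0.10, the lower edge of the band.
- Expected cases: n × p = 75 × 0.10 = 7.5. The band is above 10%, so more than 7.5.
- P(no case) = (1 − p)^n = 0.90^75 = 0.0004, so P(at least one) = 0.9996.
- For contrast, at an assumed rate of 1%: 75 × 0.01 = 0.75 expected cases and P(at least one) = 1 − 0.99^75 = 0.53.

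Each such case would meet the permanent-damage criterion in Section 10.2.1.

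**4. Could the trial check the band?** Exact (Clopper-Pearson) 95% intervals for the Study Arm, if all 75 were asked:
- 0 of 75: upper limit 1 − 0.025^(1/75) = 4.8%.
- 3 of 75: 0.8% to 11.2%.
- 8 of 75: 4.7% to 19.9%.

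Damage caused at surgery that is truly permanent must still be present at 180 days. A very low count then would therefore speak against a rate above 10%. A high count would not establish permanence, because follow-up of about 180 days ends where the stated numbness range ends. The control arm is small: with 0 of 25, the upper limit is 1 − 0.025^(1/25) = 13.7%. The comparison would be descriptive.

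**5. What the planned assessments would catch.**
- *Allodynia pathway:* increased sensitivity in screen-positive subjects of either arm. A numb area has no response category in Appendix 2. Section 7.1 lists no baseline sensory test.
- *Adverse event pathway:* numbness could be recorded at either call. It reaches the eCRF only if judged related to cryoanalgesia or the device, and the planned summary has no control column.

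Neither pathway yields a count of lasting sensory loss by arm.

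**The case against.** The strongest reply is that this is an editing matter in an appendix and that the trial already looks at sensation. Much of that stands, and it rules out several stronger readings that a reader might infer.

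- *That the figures contradict each other.* There is one figure. The other passages are qualitative.
- *That the Introduction denies long-term nerve damage.* It speaks of histological damage, which is narrower than changed sensation, and says what the technique can produce.
- *That Section 10.0 treats the harm only as temporary.* It also lists permanent nerve damage.
- *That the late calls cover allodynia alone.* Both list an adverse event assessment. The wording of the allodynia screening questions is not in the documents, so what they omit is unknown.
- *That the trial does not measure the harm.* A difference in sensation includes allodynia, which is compared between arms, with a blinded examiner for the cotton-tip test. Nerve damage judged related would be listed for the Study Group.
- *That the risk/benefit conclusion rests on the band.* Appendix 3 states the conclusion as a belief of the sponsor and investigators and cites no frequency.

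It is also fair to say that 7.5 only restates the band as a count and is not evidence of missed cases. What the reply does not answer is the unsourced band for a permanent injury under a minimal-risk label, or the lack of a dedicated, two-arm assessment of sensory loss.

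**Conclusion.** The point holds in two parts. First, the risk statements must be reconciled. The documents do not show which is right, and this review takes no position on it. The matter goes beyond wording, because the literal band implies more than 7.5 expected serious adverse events among 75 treated subjects. That size assumes the full 75 are enrolled and that the band means what it says.

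Second, measurement of lasting sensory loss is incomplete, not absent. Hypersensitivity is covered in both arms through a screen. Sensory loss depends on adverse event reporting filtered by relatedness and summarised in one arm. This rests on the assessments as described; if the screening questions already ask about numbness in both arms, the gap narrows to recording and tabulating the answers.

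This should be corrected. It does not touch the co-primary endpoints or the sample size.

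**What to change.** 1. Reconcile the frequency band, the permanence and the risk category across the Synopsis (Indication of Device), Section 1.0, Section 10.0 and Appendix 3. Cite the source of any frequency kept, or state that none is available.
2. Add one question on numbness or altered sensation at the surgical site to the 90- and 180-day calls, put to every subject in both arms regardless of the allodynia screen and of judged relatedness.
3. Tabulate the answers by arm and visit, with the number asked and exact 95% confidence intervals, as a descriptive result. Report the 180-day figure as persistence at about six months, not as permanence.

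The cost is a text correction and one extra eCRF field at calls already scheduled. No new visit is needed, and treatment and sample size are unchanged.
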